8.4.3 Packaging and Labelling

AP30663 will be manufactured by Onyx/IPCA, Sunderland, United Kingdom. Manufacturing, packaging, and labelling of the AP30663 drug concentrate for infusion will be performed by Recipharm AB, Stockholm, Sweden. All packaging and labelling operations will be performed according to Good Manufacturing Practice for Medicinal Products and the relevant regulatory requirements.

Packaging and labelling of the AP30663 drug concentrate vials will be performed by the central drug depot Almac (location for packaging/labelling/shipping: Craigavon, UK; back-up location for shipping: Dundalk, Ireland). Glucose solution for infusion and empty infusion bags will be centrally purchased and supplied by Almac.

Labelling by Almac will include the following:

1. Labelling of the active vial and its respective carton with a booklet label which also includes kit numbering; frozen conditions are required.
2. Production of another carton (kit) which will contain a 500 mL bag of 5% glucose and an empty infusion bag. The label on the carton and the additional booklet label for the empty infusion bag will have additional text/numbering.

Almac Clinical Services will also provide labels for the infusion bags that will be shipped to the investigational site and labelled by unblinded site staff.

8.4.4 Method of Assigning Patients to Treatment Groups

For Part 1 of the study, eligible patients will be randomised 1:1 (approximately 36 patients randomised to AP30663 or placebo). An additional 18 to 72 patients will be randomised cumulatively in a 2:1 ratio to 1 or more doses of AP30663 (dependent on dose arms open at time of randomisation) or placebo in Part 2 using an interactive web randomisation system (IWRS).

Two separate lists will be utilised for the study, one for Part 1 and a separate one for Part 2. Both lists will be provided by a separate unblinded biostatistical team and provided to the IWRS.

8.4.5 Selection of Doses in the Study

The patients randomised to the active treatment arm in Part 1 of the study will be given an AP30663 dose of 3 mg/kg.

In Part 2, patients randomised to AP30663 may receive one of the following AP30663 doses: 2, 4, 5, or 6 mg/kg. The final decision on AP30663 doses for Part 2 of the study will be taken based on the DMC recommendation based on review of the IAs.

Further details on study design options and associated AP30663 dose levels in Part 2 of the study are described in [Section 8.1](#).

A justification for the selection of AP30663 doses is given in [Section 8.2.1](#).

8.4.6 Selection and Timing of Dose for Each Patient

Patients will be randomly allocated to receive either AP30663 or placebo. Each patient will receive a single intravenous infusion of either AP30663 or placebo on Day 1.

Details of duration of infusion, instructions for infusion, and dose levels before and after the IAs are included in [Section 8.4.1](#).

Calculation of individual doses based on the patient's body weight is described in [Section 8.4.2](#).

8.4.7 Blinding

This is a double-blind study. Acesion Pharma, investigators, and patients will remain blinded to the study treatment allocation until the end of the study. The randomisation list will be kept secure from the study team, investigators, and patients throughout the conduct of the study and until unblinding is authorised by Acesion Pharma and the blinded lead study statistician. The DMC will be unblinded according to the DMC Charter, and a separate unblinded statistical team will be assigned to provide the

analyses to the DMC. Further details of blinded and unblinded personnel will be included in the DMC Charter.

One or more unblinded site staff will be identified at each centre, whose role will be limited to handling the study treatment. Treatment allocation via the IWRS will be provided only to the unblinded site staff and will be sent to the pre-specified fax/email accessible only to unblinded team members.

The unblinded site staff will prepare infusion bags of AP30663 and placebo, label the final infusion bags, and provide them to the investigator in a blinded manner. This procedure is described in the pharmacy manual.

The assessors (e.g. the investigators and site personnel assessing safety and efficacy) as well as the study patients must remain blinded to the treatment assignments throughout the study.

The only planned unblinding other than at the IAs will be at the conclusion of the study, when the database has been cleaned, statistical populations have been defined, and approval for database lock has been given by Acesion Pharma.

The IWRS will be programmed with blind-breaking instructions. The study blind may be broken if, in the opinion of the investigator, it is in the participant's best interest to know the study treatment assignment. Acesion Pharma must be notified before the blind is broken unless identification of the study treatment is required for a medical emergency in which the knowledge of the specific blinded study treatment will affect the immediate management of the participant's condition (e.g. antidote is available). In this case, Acesion Pharma must be notified within 24 h after breaking the blind. The date and reason for breaking the blind must be recorded in the source documentation and eCRF, as applicable.

In case of an SAE that is unexpected and suspected to be causally related to the study drug and that potentially requires expedited reporting to regulatory authorities, the treatment code will be broken for the individual patient by the Safety and Pharmacovigilance Department.

8.4.8 Prior and Concomitant Therapy

Prior therapy with any prescribed/over-the-counter medications within 14 days prior to screening, as well as with all current medications and those initiated after signing of ICF should be recorded as concomitant therapy.

When the patient requires anticoagulation because of an AF episode, anticoagulation should be initiated and maintained according to the current international and national guidelines.

Patients with low potassium or magnesium levels at screening may be appropriately supplemented with potassium or magnesium, respectively, before baseline, according to the local standards. A re-test of the potassium level is required. The patient can be randomised after the potassium has returned to reference range (3.5 to 5.3 mmol/L).

The investigator should consult the medical monitor if there is any uncertainty regarding patient use of a particular drug or drug class.

8.4.8.1 Prohibited Medication and Procedures

[Table 2](#) provides a listing of specific restrictions for concomitant therapy use, with all necessary washout periods described. The table provides examples of prohibited drug categories; however, it is not a comprehensive list of all restricted medications.

If, before the start of study drug infusion, there is a clinical indication in a randomised patient for any therapy that is specifically prohibited, the patient should be discontinued from the study.

Use of prohibited medications and procedures for treatment of AEs in randomised patients after the end of infusion is allowed at the investigator's discretion and is not regarded as a protocol deviation.

The investigator should actively discuss any questions regarding prohibited medications/procedures with the medical monitor before randomising the patient to study treatment or before study treatment initiation.

Table 2 Prohibited Medication

Drug class/ specific compound	Examples* (including but not limited to)	Washout period/comments
Antiarrhythmic class I	Examples: ajmaline, disopyramide, flecainide, lidocaine, mexiletine, quinidine, phenytoin, prajmaline, procainamide, propafenone, tocainide	7 days before randomisation and until the completion of the Day 2 visit.
Antiarrhythmic class III	Examples: dofetilide, dronedarone, ibutilide, sotalol,	7 days before randomisation and until the completion of the Day 2 visit.
Amiodarone	Amiodarone	12 weeks before randomisation and until the completion of the Day 2 visit.
CYP3A4 inhibitors	Examples: cannabinoids, clarithromycin, cimethidine, cyclosporine, dexamethasone, diltiazem, disulfiram, doxycycline, fluoxetine, itraconazole, ketoconazole, loperamide, metronidazole, naloxone, nefazodone, norfloxacin, sertraline, terfenadine, valproic acid, voriconazole, several antiretroviral drugs	10 days and until the completion of the Day 2 visit.
Loop diuretics	Examples: bumetanide, ethacrynic acid, furosemide, torsemide	Anticipated change in dose or initiation dose is prohibited from screening visit to the end of the infusion
QT-prolonging drugs	Examples: azithromycin, clarithromycin, erythromycin, roxithromycin, fluconazole, ketoconazole, chloroquine, amitriptyline, doxepin, imipramine, haloperidol, risperidone, clozapine, pimozide, droperidol, terfenadine, astemizole, probucol, cisapride	10 days and until the completion of the Day 2 visit.
St John's Wort	-	10 days and until the completion of the Day 2 visit.
Any other investigational drug		3 months before randomisation and during the study
AP30663		Any previous administration

*Please consult the prescription information of a specific drug for more details.

The following procedures are prohibited:

1. Any cardioversion attempt of AF or atrial flutter within 1 week preceding randomisation.
2. Prior failed attempt (no conversion) of pharmacological or DC cardioversion of previous or current AF episode.
3. Significant surgical procedure within 4 weeks preceding the screening visit.
4. Pacemaker or implantable cardioverter defibrillator therapy prior to randomisation and during the treatment phase of the study.
5. Myocardial revascularisation (PCI or CABG) or other revascularisation procedure during the last 6 weeks before randomisation.

8.4.8.2 Rescue Medication

All patients who will not convert from AF during infusion of the study drug or within 90 min after the infusion start should undergo DC electrical cardioversion within 180 min from the time the infusion started. DC electrical cardioversion should be performed using biphasic synchronised cardioverter with energy of 200 J.

All medications necessary for direct-current electrical cardioversion (e.g. sedatives) should be administered per local standards, observing limitations from [Section 8.4.8.1](#) (Prohibited Medication and Procedures), and should be recorded as concomitant medications.

8.4.9 Treatment Compliance

The study drug will only be applied by the investigator on Day 1. The timing and duration of the infusion as well as the dose calculation depending on the patient's weight will be noted in the patient's medical file and recorded in the eCRF (day of application). Early termination of infusion and reason for termination will also be recorded in the eCRF.

9 TIMING OF STUDY PROCEDURES

The planned study assessments are listed in [Section 8.1.2](#).

9.1 Screening Visit

Patients will need to provide written informed consent before any study-related procedures are performed.

- Record any AEs that have occurred and any changes in concomitant medication since signing of the informed consent.
- Assess for eligibility (against the inclusion and exclusion criteria).
- Collect full medical and surgical history, including concomitant illnesses/diseases and concomitant medications.
- Record demographic data, such as date of birth or age (according to applicable regulations), ethnic origin, and sex.
- Perform a full physical examination, including body weight and height.
- Record vital signs ([semi]supine BP, heart rate, heart rhythm from ECG).
- Collect blood samples for haematology and clinical chemistry (refer to the Schedule of Assessments in [Section 8.1.2](#) for parameters included), urea (blood urea nitrogen [BUN]), electrolytes (magnesium, sodium, calcium, potassium), International normalised ratio (INR)/activated partial thromboplastin time (APTT), and thyroid stimulating hormone (TSH).

Note:

If TSH levels were tested within 1 week before randomisation at a local laboratory certified for the study, those results will be acceptable and should not be re-tested at screening.

One coagulation parameter (either INR or APTT) is required for an individual patient. The investigator should decide which parameter is relevant for a given patient, taken into consideration clinical presentation and concomitant medications used by that patient. The same coagulation parameter should be consistently analysed throughout the study in an individual patient.

- Perform a 12-lead ECG.
- Perform a transthoracic echo (TTE) if TTE done within 6 months (inclusive) is not available.

9.2 Day 1 – Pre-infusion (Baseline)

The baseline visit on Day 1 with pre-infusion assessments will take place within 7 days of onset of AF. The following procedures will be performed at the baseline visit prior to study drug infusion:

- Reassess for eligibility against the inclusion and exclusion criteria.
- Randomisation¹ will take place for eligible patients, and each will be assigned a patient number.
- Record any AEs that have occurred and any changes in concomitant medication since the previous visit.
- Perform a brief physical examination (general appearance, cardiovascular, respiratory, gastrointestinal, other).
- Record vital signs ([semi]supine BP, heart rate, heart rhythm from ECG).
- Collect blood samples for haematology and clinical chemistry (refer to the Schedule of Assessments in [Section 8.1.2](#) for parameters included) if not already assessed <72 h before baseline.
- Collect blood sample for INR/APTT for all patients on heparin or vitamin K antagonists when screening >24 h before start of infusion.
- Collect baseline PK plasma sample.
- Perform a 12-lead ECG with ECG print-outs within 15 min before infusion start. Confirm diagnosis of AF (defined as absence of discrete P waves and an irregular ventricular rate) based on the 12-lead ECG. If QTcF is above 450 ms the infusion should not be initiated.
- Perform 12-lead Holter monitoring (start 30 min before infusion start).
- Perform telemetry (start 30 min before infusion start).

9.3 Day 1 – During Infusion

When all the baseline procedures have been performed and the investigator has confirmed the patient's eligibility for the study, study drug will be administered as a single intravenous infusion for 30 min on Day 1. The following procedures will be performed during infusion on Day 1:

- Administer study drug as intravenous infusion.

¹ Note, if the patient is found eligible, the randomisation should be planned in such a way that all logistics will occur in the protocol-specified timeframe, including timely reconstitution of study drug, infusion start and – if applicable - DC cardioversion in non-responders within 180 min from infusion start.

- Record any AEs that have occurred since the pre-infusion status and any changes in concomitant medication. Special attention should be paid to monitoring for AEs related to the central nervous system including tremors. Please also refer to section 8.2.4.2 for stop of infusion criteria.
- Record vital signs ([semi]supine BP, heart rate, heart rhythm from ECG).
- Collect PK plasma samples 5 min \pm 1 min, 15 min \pm 1 min, 25 min \pm 1 min, and 30 min - 1 min after start of infusion. The infusion should not be stopped before the 30 min - 1 min PK sample has been collected. In the case of conversion from atrial fibrillation during infusion, an additional PK sample will be taken immediately after conversion.
- Perform a 12-lead digital ECG (with ECG print-outs 10 min after infusion start and, in case of conversion from AF, within 1 min after conversion BUT before infusion stop).
- Continue 12-lead Holter monitoring.
- Continue telemetry.

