- d Haematology parameters include haemoglobin, haematocrit, red blood cells (erythrocytes), white blood cells (leukocytes, total and differential), basophils, eosinophils, lymphocytes, monocytes, neutrophils, and platelets.
- e Additional haematology and clinical chemistry parameters will be evaluated if not already assessed <72 h before start of infusion.
- f Clinical chemistry parameters include ALT, AST, bilirubin creatinine, GGT, glucose (random), and eGFR.
- g Only one coagulation parameter (either INR or APTT) is required for an individual patient. The same coagulation parameter should be consistently analysed throughout the study in an individual patient.
- h Patients with low potassium levels at screening may be supplemented with potassium. A retest is required before randomisation.
- i To be repeated for all patients on heparin or vitamin K antagonists when screening >24 h before start of infusion.
- j If TSH levels were tested within 1 week before randomisation at a local laboratory certified for the study, those results will be acceptable and should not be re-tested at screening.
- k Randomisation must occur as soon as possible between 3 h and 7 days (inclusive) after start of the current AF episode. Each randomised patient will be assigned a patient number. Note, if the patient is found eligible, the randomisation should be planned in such a way that all logistics will occur in the protocol-specified timeframes including timely reconstitution of study drug, infusion start and, if applicable, direct-current cardioversion in non-responders.

- 1 Study drugs must be administered as soon as possible after randomisation and preferably not later than 12 h after randomisation.
- m Plasma samples will be taken at baseline (pre-infusion) and at the following time points after start of infusion: 5 min \pm 1 min, 15 min \pm 1 min, 25 min \pm 1 min, 30 min - 1 min (the infusion will not be stopped before the 30-min PK sample has been collected), 45 min \pm 5 min, 1 h \pm 5 min, 1 h 30 min \pm 5 min, 4 h \pm 5 min, 8 h \pm 5 min, and 24 h \pm 2h. In the case of conversion from atrial fibrillation within 90 min from the start of infusion, an additional sample will be taken immediately after conversion.

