8.2 Discussion of Study Design

8.2.1 Study Rationale

This is a proof-of-concept study aiming to show the ability of AP30663 to terminate ongoing AF episodes.

The study was designed to allow for modifications to the AP30663 dose without undermining the validity and integrity of this study. After all randomised patients have completed Day 2 assessments of the study (or terminated), an interim analysis will be conducted to determine whether or not the study can be continued to Part 2 and, if to be continued, to determine the starting dose(s) of AP30663 to be used in Part 2 of the study. Further IAs will be conducted during Part 2 to allow for additional doses to be tested, or poor-performing doses to be stopped. This is expected to determine a dose of AP30663 with adequate efficacy and minimal adverse effects. No Type II error correction will be taken into account due to this being a proof-of-concept study.

Choice of placebo comparator

Currently, there is no gold standard treatment for AF in the EU and the recommended first-line agents are only moderately effective. A placebo group was chosen as control group to prevent bias and as there is no standard treatment for AF in the EU. Treatment with placebo is short (30 min infusion) and patients will receive DC electrical cardioversion if AF is still ongoing 90 min after the infusion start.

Rationale for dose selection

In the completed phase 1 trials a dose and plasma concentration related effect on QTcF was found with a peak estimated mean QTcF prolongation of 45.2 ms for the dose of 6 mg/kg. The QTcF effect was transient and a return to baseline level was observed 8 hours after the start of administration for the 6 mg/kg dose consistent with low plasma concentrations at this timepoint. No other dose related effects were found.

For the starting dose of 3 mg/kg preclinical data support the assumption that it will result in a sufficiently high free plasma concentration to be effective in conversion.

The increase of the QTcF would serve as a safety parameter, but might also be a marker of a higher increase of the atrial effective refractory period (AERP) and thereby be indicative of a higher chance of conversion. In this study, the continuous monitoring of the patients during and after the 30-minute infusion in combination with predefined stopping criteria (see [Section 8.3.4.2](#)) will guarantee the safety of the patients.

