8.2.2 Quality Management and Risk Evaluation

This protocol was evaluated to identify those processes and data that were critical to ensure human patient protection and reliability of study results.

Risk control measures will be periodically reviewed to ascertain whether the implemented quality management activities remain effective and relevant, taking into account emerging knowledge and experience.

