8.3.4.2 Treatment Discontinuation (Stop of Infusion)

The planned duration of drug infusion is described in [Section 8.4.1](#).

Criteria for stop of drug infusion prior to cardioversion or prior to the infusion duration of 30 min are as follows:

- Developing hemodynamic instability (drop in BP, drop in heart rate, unless caused by conversion) including but not limited to
 - systolic BP decrease to <90 mm Hg or significant decrease from baseline (e.g. >40 mm Hg), or mean BP decrease <70 mm Hg (calculated as [systolic BP + 2 × diastolic BP] / 3).
 - systolic BP increase to >190 mm Hg or
 - heart rate <40 bpm or
 - intolerable side effects.
- Developing changes in ECG variables (compared with pre-infusion ECG):
 - QRS +50% and/or development of BBB.
 - QTcF +60 ms.
 - QTcF >500 ms.
- Developing tremors (involuntary, rhythmic muscle contraction leading to shaking movements in one or more parts of the body)
- Per investigator decision, when it is not in the patient's best interest to continue infusion. Specific attention should be paid to any other AEs related to the central nervous system and/or any local infusion site reactions.

Pregnancy

Patients will be instructed that known or suspected pregnancy occurring during the study, in female patients or female partners of male patients, should be confirmed and reported to the investigator. The investigator should also be notified of any pregnancy occurring during the study but confirmed only after completion of the study. In the event that a patient is subsequently found to be pregnant after inclusion in the study, any pregnancy will be followed to term, and the status of mother and child will be reported to Acesion Pharma after delivery.

Full details will be recorded in the eCRF and a pregnancy reporting form will be completed (see [Section 10.1.3.1.1](#)).

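### Protocol 9.3 and Schedule footnote m bar stopping the infusion before the 30-minute PK sample with no safety exception, and the 9.3 pointer to the stop criteria cites a section that does not exist

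*Protocol*

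**What the plan says.** Two site-facing sentences tie the end of the infusion to the 30-minute PK sample. Protocol 9.3 (Day 1, during infusion) states: "The infusion should not be stopped before the 30 min - 1 min PK sample has been collected". Footnote m of the Schedule of Assessments (8.1.2) is firmer: "the infusion will not be stopped before the 30-min PK sample has been collected". SAP 9.1 repeats the rule when it describes the sampling schedule.

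Protocol 8.3.4.2 provides for the opposite action. It opens with "Criteria for stop of drug infusion prior to cardioversion or prior to the infusion duration of 30 min are as follows" and then lists haemodynamic limits, QRS and QTcF changes, tremors and investigator judgement. It does not mention the PK sample.

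An earlier bullet in 9.3 directs staff to those criteria: "Please also refer to section 8.2.4.2 for stop of infusion criteria".

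Section 8.2.1 makes patient safety depend on "the continuous monitoring of the patients during and after the 30-minute infusion in combination with predefined stopping criteria". Section 8.4.9 expects that some infusions will end early: "Early termination of infusion and reason for termination will also be recorded in the eCRF".

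**The concern.** A nurse or investigator who follows 9.3 or footnote m literally would keep the infusion running after a stop criterion had been met, in order to obtain a PK sample. The criteria exist to end exposure promptly in a patient whose blood pressure, heart rate, QRS or QTcF has moved too far. The drug prolongs QTcF in relation to dose and concentration, 5 mg/kg opens by rule in Part 2, and 6 mg/kg can follow. Instructions for the infusion itself should not contain a sentence that conflicts with the safety rule. The reference in 9.3 that would settle the matter leads to a section number that is not in the document. What is at stake is conduct at the bedside, not the statistics.

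**Working it through.** The protocol gives no figure to reproduce on this point. The check sets the provisions side by side.

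1. **When the sample is due.** Protocol 9.3 and footnote m give the time as 30 min with a tolerance of minus 1 min, so the window runs from 29 to 30 min after the start of infusion.

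2. **Whether a criterion can be met before then.** Section 9.3 itself schedules a 12-lead ECG, "with ECG print-outs 10 min after infusion start". That is 29 − 10 = 19 min before the window opens. Telemetry runs throughout, and the blood pressure, heart rate and tremor criteria can be met at any time.

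3. **A worked case.** Suppose the 10-minute ECG shows QTcF 60 ms above the pre-infusion value.
   - Under 8.3.4.2, this is a criterion for stopping the infusion.
   - Under the literal wording of 9.3 and footnote m, the infusion continues until the sample has been drawn, at 29 min at the earliest.
   - Both cannot be done.

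4. **Whether either sentence carries an exception.** Of the two site-facing sentences, none does. SAP 9.1 has none either, but it does not direct bedside conduct.

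5. **Whether the pointer resolves.** Section 8.2 contains 8.2.1 and then "8.2.2 Quality Management and Risk Evaluation"; the next heading is 8.3. The table of contents agrees, so there is no 8.2.4.2. The criteria are in 8.3.4.2, which 8.2.1 cites correctly. Footnote m has no pointer at all.

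6. **Whether meeting a criterion is plausible.** Sections 6 and 8.2.1 report a peak estimated mean QTcF prolongation of 45.2 ms at 6 mg/kg in the Phase 1 trials, which section 6 says were in healthy men. The stop criterion is +60 ms, a margin of 60 − 45.2 = 14.8 ms above that mean. The documents give no between-patient spread and do not say how much of the effect is present before 29 min, so no frequency can be derived and none is claimed.

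**The case against.** The strongest reply is that the conflict comes from reading one sentence out of context. In footnote m the wording is a parenthesis attached to the 30-minute sample, and in 9.3 it follows the same time point. The natural meaning is to draw the sample and then switch off. It may also mean that the infusion should not be cut short merely because the patient has converted. Neither reading overrides a safety stop. Section 8.3.4.2 is the specific rule on stopping before 30 min and includes investigator judgement. Section 9.3 says should rather than must, and it names the stop criteria before it reaches the PK sentence. Early stops are foreseen in 8.4.9, in the adverse-event action categories and in SAP 10.2. The wrong section number is easy to work out from the table of contents. Detailed instructions also sit in a Study Drug Administration Manual that is not available here.

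Most of this stands, and it is why the severity is low. It is also fair that the hazard exception for deviations in Protocol 11.3 is beside the point: a stop under 8.3.4.2 carries out the protocol and should not need to be excused as a deviation.

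The reply does not supply the missing exception or make the pointer correct. Nor do the documents consistently treat a criterion-driven stop as compliant. SAP 5.7 lists stopping before 30 min among its examples of major deviations, under noncompliance with study medication, and does not exempt stops required by 8.3.4.2.

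**Conclusion.** The point holds at low severity. As written, two of the protocol's instructions for infusion day contradict the early-stop criteria for any patient who meets one before the sample window opens at 29 min, and one cross-reference is wrong. The wrong section number is an error on any reading. The contradiction depends on a literal reading of the PK sentences, which was probably not intended, and a clinician would most likely stop the infusion anyway. How often the situation would arise cannot be judged from the documents, and the unseen administration manual may already set the order of events. The endpoint, sample size and primary analysis are unaffected.

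**What to change.** In Protocol 9.3 and Schedule footnote m, add to the PK sentence: *unless a stop criterion in Section 8.3.4.2 is met*. Make the same addition in SAP 9.1 for consistency only. In 9.3, change the cross-reference from 8.2.4.2 to 8.3.4.2.

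The cost is one clause in two protocol places, the same clause once in the SAP, and one section number. Nothing in the design or analysis changes. A patient stopped early under the criteria may lack an end-of-infusion sample at the nominal time. Protocol 11.1.5 already allows PK parameters to be estimated from the remaining samples where possible.
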